### **2.3.4 Clinical Experience**

Excluding the current study ISIS 396443-CS4, 9 additional clinical studies with ISIS 396443 have been initiated: 3 studies have been completed and 6 are ongoing. Four (4) of the clinical studies are in patients with “later-onset SMA,” 2 trials are in “infantile-onset (Type I) SMA,” 1 trial is in neonates and infants with genetically diagnosed and presymptomatic SMA, and 2 trials are in both “infantile-onset” and “later-onset” populations. The ISIS 396443 clinical studies are described in detail in the Investigator's Brochure and listed here:

- ISIS 396443-CS1 (completed): an open-label, single ascending-dose (SAD) Phase 1 study designed to assess the safety, tolerability and pharmacokinetics of ISIS 396443 in patients with SMA, aged 2 to 14 years
- ISIS 396443-CS2 (completed): an open-label, multiple ascending-dose (MAD) Phase 1/2a study designed to assess the safety, tolerability and pharmacokinetics of ISIS 396443 in patients with SMA, aged 2 to 15 years
- ISIS 396443-CS10 (completed): an open-label Phase 1 study to assess the safety and tolerability of a single IT dose (6 or 9 mg) of ISIS 396443 in patients with SMA who previously participated in ISIS 396443-CS1
- ISIS 396443 CS12 (ongoing): an open-label Phase 2 study to assess the safety and tolerability of a single IT dose (12 mg) of ISIS 396443 in patients with SMA who previously participated in either ISIS 396443 CS2 or ISIS 396443-CS10
- ISIS 396443-CS3A (ongoing): a multiple-dose Phase 2 study designed to assess the safety, tolerability, pharmacokinetics and efficacy of ISIS 396443 in patients with infantile-onset SMA (symptomatic SMA infants < 7 months of age)

- ISIS 396443-CS3B (ongoing): a Phase 3 randomized, double-blind, sham-procedure controlled study to assess the clinical efficacy, safety, tolerability and pharmacokinetics of ISIS 396443 in patients with infantile-onset SMA
- ISIS 396443-CS5 (232SM201: ongoing): an open-label Phase 2 study to assess the efficacy, safety, tolerability, and pharmacokinetics of multiple doses of ISIS 396443 delivered intrathecally to subjects with genetically diagnosed and presymptomatic SMA
- ISIS 396443-CS7 (232SM202: ongoing): a Phase 2, randomized, double-blind, sham-procedure controlled study to assess the safety and tolerability and explore the efficacy of ISIS 396443 administrated intrathecally in subjects with SMA who are not eligible to participate in the clinical studies ISIS 396443-CS3B or ISIS 396443-CS4
- ISIS 396443-CS11 (ongoing): an open-label Phase 3 extension study for patients with SMA who previously participated in investigational studies of ISIS 396443. Safety and tolerability will be assessed in this study. Up to 274 patients from ISIS 396443-CS3B, ISIS 396443-CS4, and ISIS 396443-CS12 are eligible to enroll

## 2.4 Rationale for Dose and Schedule of Administration

The proposed study will test the clinical efficacy, safety, tolerability, and PK of multiple doses of ISIS 396443 administered as IT injections to subjects with later-onset SMA. A single dose level of 12 mg ISIS 396443 will be evaluated, delivered as 4 doses administered over 9 months. ISIS 396443 will be administered using a loading regimen (dosings on Study Days 1, 29, 85) followed by maintenance dosing given 6 months thereafter (dosing on Study Day 274).

The ISIS 396443-CS4 dose level and dose interval was selected based on preclinical toxicology and pharmacokinetic observations from monkey studies utilizing single-dose and repeat dosing IT administration, consideration of the target tissue concentration anticipated for drug pharmacology, and safety data in the completed and ongoing clinical studies of ISIS 396443 to date. Based upon pharmacology and pharmacokinetic results in SMA transgenic mice, we estimate that the target tissue concentration to produce 50 to 90% SMN2 Exon 7 inclusion is between 1 and 10  $\mu$ g/g spinal cord tissue. Nonclinical studies in juvenile monkeys receiving IT doses of ISIS 396443 showed a resulting gradient of distribution of ISIS 396443 along the spinal cord, with mean lumbar spinal cord concentrations ranging from 1.6-2.3 fold and 2.0-3.5 fold higher than thoracic and cervical spinal cord levels, respectively. The dose level selected for this multiple-dose clinical study (12 mg ISIS 396443) is predicted to achieve levels at the high end of this range (approximately 10  $\mu$ g/g lumbar and 3  $\mu$ g/g cervical spinal cord tissue concentrations), following the first dose. The loading dose interval was selected based on the nonclinical pharmacokinetic and pharmacology data as the dose interval to achieve and maintain ISIS 396443 spinal cord tissue levels that are predicted to be within the upper end of the pharmacologically active range by Day 85 (predicted to be approximately 24  $\mu$ g/g lumbar and 8  $\mu$ g/g cervical tissue concentration), while at the same time considering subject safety and convenience for repeated LP intrathecal injections. The maintenance dose interval (once every 6 months) was selected based on the estimated spinal tissue and CSF drug half-life (4-6 months) and was selected to maintain spinal cord tissue levels of ISIS 396443 at a steady-state level within the estimated pharmacologically active range.

Additional details on dose scaling and expected CSF and tissue concentrations are summarized in the Investigator's Brochure.

### **3. EXPERIMENTAL PLAN**

#### **3.1 Study Design**

This is a Phase 3 multicenter, double-blind, randomized, sham-procedure controlled study of ISIS 396443 in patients with later-onset SMA studied for 15 months. Approximately 117 subjects will be randomized 2:1 to receive 12 mg dose ISIS 396443 or a sham procedure control, respectively. ISIS 396443 will be administered using a loading regime (dosings on Study Days 1, 29, and 85) followed by a maintenance dose 6 months thereafter (dosing on Study Day 274).

Randomization will be stratified based on:

1. Subject's Age at Screening (< 6 years vs.  $\geq$  6 years)

Following treatment and the Day 456 follow-up evaluation, all eligible subjects may elect to enroll in an open-label treatment extension study, pending study approval by the IRB or IEC and the appropriate regulatory authority. This will be done without unblinding to subject's treatment group.

An interim analysis may take place when all subjects have completed the 6-month assessment and at least 39 subjects have completed the 15-month assessment. In the event of a decision by the study Sponsor to terminate the study earlier on the grounds that conducting a sham-controlled study is no longer deemed ethical based on an updated risk benefit assessment of ISIS 396443 from the planned interim analysis, all subjects will be invited for the end-of-double-blind-period (EODBP) study visit, during which all Day 456 assessments will be conducted. After completing the EODBP visit, subjects will be considered study completers and will be allowed to enroll into the open-label extension study.

#### **3.2 Number of Study Centers**

This study will be conducted at multiple centers worldwide.

#### **3.3 Number of Subjects**

Approximately 117 subjects (2 ISIS 396443; 1 sham-procedure) will receive 12 mg dose of ISIS 396443 or a sham procedure control. The total number of subjects randomized may be higher if some subjects do not receive their Day 1 dose/sham procedure. The maximum number of subjects will not exceed 130.

#### **3.4 Overall Study Duration and Follow-up**

The Study will consist of screening, treatment, and post-treatment follow-up-periods. The total duration of participation in the study is approximately 16 months. Please refer to the Schedule of Procedures in [Appendix A](#).

### **3.4.1 Screening**

After informed consent/assent is obtained, subjects will undergo a screening evaluation no greater than 28 days prior to first dose administration at which their eligibility for the study will be examined.

### **3.4.2 Treatment**

Subjects who meet the eligibility criteria will be admitted to the study center on Study Day 1, undergo pre-dose evaluations, be randomized, and then receive either an LP injection of Study Drug (ISIS 396443) or a sham procedure. Subjects will return to the study center on Days 29, 85, and 274 for follow-up evaluations and subsequent injections/sham procedures. Following the injection/sham procedure on Day 1, subjects will remain at the study center for at least 24 hours post-procedure for safety monitoring. Following the injection/sham procedure on Day 29, 85, and 274 subjects will remain at the study center for at least 6 hours post-procedure for safety monitoring. Safety monitoring visits will occur Study Days 30, 86, 92, 169, and 275 (through the last injection/sham procedure). In addition, the study center will monitor the subject's condition through telephone contact on a monthly basis.

For subjects receiving ISIS 396443, a CSF sample for PK and SMN protein analyses will be taken pre-dose on each injection day in a manner that protects the blind.

If a subject terminates early from the study, they will be encouraged to complete assessments per the Day 456 visit. If a subject is randomized but does not successfully receive the first dose of ISIS 396443/undergo the first sham procedure, they will be replaced.

### **3.4.3 Post-Treatment Follow-up**

After completion of the Day 275 visit, subjects will enter the 6-month post-treatment evaluation period. This period consists of Study Center visits on Day 365 and 456 and follow-up phone assessments on a monthly basis, as outlined in the Schedule of Procedures ([Appendix A](#)). After completion of the Day 456 visit, subjects may be eligible to participate in an OLE study, pending study approval by the IRB or IEC and the appropriate regulatory authority.

## **3.5 End-of-Study**

The End-of-Study is last subject; last visit (either in-person visit or telephone contact). In the event of a decision by the study Sponsor to terminate the study earlier on the grounds that conducting a sham-controlled study is no longer deemed ethical based on an updated risk-benefit assessment of ISIS 396443 from the planned interim analysis, all subjects will be invited for the EODBP study visit, during which all Day 456 assessments will be conducted. The EODBP visit should occur no less than 2 weeks from the most recent dosing/sham procedure administered. After completing the EODBP visit, subjects will be considered study completers and will be allowed to enroll into the OLE study.

## **3.6 Safety Monitoring and Data Safety Monitoring Board**

Safety data will be reviewed on an ongoing basis by the Sponsor and the Medical Monitor. Safety data will also be reviewed on a quarterly basis by an independent data and safety monitoring board (DSMB). The DSMB will be assembled to review safety, tolerability and efficacy (as needed) data collected on ISIS 396443 during this study. Based on its ongoing

assessment of the data, the DSMB will provide recommendations to the Sponsor for modifying, stopping or continuing the study.

## **4. SUBJECT ENROLLMENT**

### **4.1 Screening**

Before subjects may be enrolled into the study, the Sponsor requires a copy of the Study Center's written IRB or IEC approval of the protocol, informed consent form, informed assent form (if applicable) and all other subject information and/or recruitment material.

Before a subject's participation in the trial, the Investigator is responsible for obtaining written informed consent from the parent(s) or legal guardian(s) and, in cases where institutional guidelines and the patient's age dictate, informed assent from the subject. At the time of consent/assent, the subject will be considered enrolled into the study and will be assigned a unique screening number before any study procedures, including screening procedures, are performed. The screening number must remain constant throughout the entire trial. In the event the subject is re-consented and re-screened the subject must be given a new screening number. Screening numbers, once assigned, will not be re-used.

### **4.2 Randomization**

Subjects will be randomized after all screening assessments have been completed and after the Investigator and the Medical Monitor have verified that they are eligible per criteria in [Sections 5.1 and 5.2](#). No subject may begin treatment prior to randomization and assignment of a unique randomization number.

Using an Interactive Voice/Web-Response System (IXRS), eligible subjects will be randomized 2:1 to receive ISIS 396443 or sham-procedure control, respectively. Randomization will be stratified for:

- Subject's Age at Screening (< 6 years vs.  $\geq$  6 years)

The Sponsor Quality Assurance department or designee will hold a copy of the randomization lists generated by the IXRS vendor.

### **4.3 Replacement of Subjects**

If a subject does not successfully receive the first dose of ISIS 396443/undergo the first sham procedure, they will be replaced.

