## 8. TREATMENT OF SUBJECTS

### 8.1 Study Drug Administration

Details regarding the LP dosing injection procedure will be provided in the Dosing Administration Manual. ISIS 396443 will be administered by dedicated study personnel who are unblinded to treatment group; this cannot be any of the key study site personnel (i.e., the Principal Investigator, study coordinator, or outcomes assessors). The Study Drug administration will be performed in a dedicated room and the key study personnel and the parents will not be present during the procedure to ensure blinding.

ISIS 396443 will be administered as an intrathecal slow bolus (1-3 minute) LP injection. ISIS 396443 will be administered using a ‘spinal anesthesia’ needle and syringe. A 22G to 25G spinal anesthesia needle is recommended, but a 21G may be used if indicated by subject size or clinical condition. The target site for needle insertion is the L3/L4 space, but may be 1 segment above or 1-2 segments below this level, if needed. The volume of the injection is 5 mL; prior to the injection 5 mL of CSF fluid is to be collected for analyses. Depending on institutional guidelines, anesthesia or sedation may be used for the LP procedure, following institutional procedures. Subjects will be encouraged to lie flat for 1-hour following dosing, if possible.

Table 2 outlines the dose, ISIS 396443 concentration, and volume for administration of ISIS 396443.

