### 8.2 Sham Procedure

Subjects randomized to the sham-procedure control group will undergo a sham-procedure, rather than Study Drug administration, on Study Days 1, 29, 85, and 274. Details regarding the sham procedure will be provided in the Dosing Administration Manual. The sham procedure will be administered by dedicated study personnel who are unblinded to treatment group; this cannot be any of the key study site personnel (i.e., the Investigator, study coordinator, or outcomes assessors). The sham procedure will be performed in a dedicated room and the key study personnel and the parents will not be present during the procedure to ensure blinding.

In general, the sham procedure will consist of a small needle prick on the lower back at the location where the LP injection is normally made. The needle will break the skin but no LP injection or needle insertion will occur. The needle prick will be covered with the same bandage that is used to cover the LP injection normally, thus simulating the appearance of an LP injection. If anesthesia or sedation is used for the LP procedure in ISIS 396443 treated subjects, then in order to maintain the blind, minimal sedation (i.e. a low dose of an anxiolytic) should be used for the sham procedure, following institutional procedures. The study subject will be kept in the procedure room for the same amount of time that subjects administered Study Drug are kept, thus simulating the time period of a Study Drug administration procedure.

Study Drug and sham kits will be packaged in a blinded fashion. Blinded kits for sham procedure contain artificial CSF (5.0 mL solution per 6 mL vial) that will not be injected but will be used to simulate CSF samples for that subject.

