**10.3 Populations**

Intent to Treat (ITT) Set: All patients who are randomized and receive at least 1-dose of Study Drug/sham procedure.

Per-Protocol Set (PPS): PPS will include the subset of the ITT who complete at least the initial 3 doses of Study Drug/sham procedures, have baseline and Day 169 efficacy assessments and who have no significant protocol deviations that would be expected to affect efficacy assessments.

Safety Set: All patients who are randomized and receive at least 1-dose of Study Drug/sham procedure.

Pharmacokinetic Population: All patients who are randomized and for which there is at least 1 evaluable post-dose/post-sham procedure pharmacokinetic sample.

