Subjects will return to the study center on Days 29, 85, and 274 for follow-up evaluations and subsequent injections/sham procedures. Following the injection/sham procedure on Day 1, subjects will remain at the study center for at least 24 hours post-procedure for safety monitoring. Following the injection/sham procedure on Days 29, 85, and 274, subjects will remain at the study center for at least 6 hours post-procedure for safety monitoring. Safety monitoring visits will occur Study Days 30, 86, 92, 169, and 275 (through the last injection/sham procedure). In addition, the study center will monitor the subject’s condition through telephone contact on a monthly basis.

For subjects receiving ISIS 396443, a CSF sample for PK analysis will be taken pre-dose on each injection day in a manner that protects the blind.

Subjects who terminate early from the study will be encouraged to complete assessments per the Day 456 visit. Subjects who are randomized but do not successfully receive the first dose of ISIS 396443/undergo the first sham procedure will be replaced. Results from these subjects will be reported in the CSR as occurring before the start of treatment and will not be included in the formal analyses.

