### 3 General considerations

In this Statistical Analysis Plan, the terms “control” and “control group” refer to the set of subjects who were randomized to undergo the sham procedure, and the terms “treatment” and “dosed” are used interchangeably to describe those subjects in the ISIS 396443 group who received at least one intrathecal injection of ISIS 396443.

In order to distinguish nominal visit names from duration defined in terms of days, visit names will be referred as “Day 29”, “Day 85,” etc., and “29 days” or “85 days,” etc. will be used to define time intervals. In the protocol definitions of the efficacy endpoints, and description of the interim analysis, “Month 6” is used to refer to “Day 169” and “Month 15” is used to refer to “Day 456” and this convention will be followed in this SAP.

The Intent-to-treat (ITT) Set and the Per-protocol Set (PPS) will be used for the efficacy analyses. The ITT Set is defined as all subjects who are randomized and received at least one dose of study drug/sham procedure. Subjects will be analyzed in the treatment group to which they were randomized. This will be the primary population for the analysis of efficacy endpoints.

An Interim Efficacy Set will be defined for presentation of the WHO motor milestone endpoints in the event an interim analysis is performed. The Interim Efficacy Set will be defined as the subset of subjects in the ITT Set who have the opportunity to be assessed at the Month 15 visit. Specifically, the Interim Efficacy Set will include all subjects with a Month 15 visit and all subjects with time difference of at least 463 days (456 plus 7 day window) between date of first dose and the targeted clinical cut-off date for the interim analysis (i.e., dosed on or before May 27, 2015). However, a subject who has died or withdrawn will be included provided that there is a time difference of at least 449 days (456 minus 7 day window) between the date of first dose and the targeted clinical cut-off date of Aug 31, 2016 for the interim analysis (i.e., dosed on or before June 10, 2015).

In the event of the study being stopped early, an Efficacy Set will be similarly defined for the analysis of motor milestones. If, however, the study continues to completion as planned, the ITT Set will be used for the final analysis of motor milestones.

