The PPS will include the subset of the ITT who complete at least the initial 3 doses of study drug/sham procedures, have baseline and Day 169 efficacy assessments and who have no significant protocol deviations that would be expected to affect efficacy assessments.

Significant protocol deviations will be determined prior to database lock but will include subjects who had onset of signs and symptoms consistent with SMA at less than or equal to 6 months of age, who cannot sit independently, whose HFMSE is <10 or >54 at screening, who had respiratory insufficiency at Screening (defined as medical necessity for invasive or non-invasive ventilation for >6 hours during a 24-hour period), and subjects who took any medicines (such as valproate, riluzole, creatine, sodium phenylbutyrate, hydroxyurea, salbutamol, olesoxime) during the study for the treatment of SMA, shown to modulate SMN gene expression or SMA disease progression in humans or preclinical models. The Safety Set, comprised of all subjects who were randomized and received at least one dose of study drug or underwent one sham procedure, will be used for the analysis of safety data. Subjects

randomized to receive sham procedure, incorrectly treated with ISIS 396443 will be counted in the ISIS 396443 group from the first dose of ISIS 396443 received.

The Pharmacokinetic Population is comprised of all subjects who were randomized and for which there is at least one evaluable post-dose/post-sham procedure pharmacokinetic sample. Analysis of immunogenicity data will also be based upon this population.

A listing denoting inclusion/exclusion of patients in all the analysis populations will be provided.

The individual sites in this multicenter study will be pooled for the purpose of statistical analysis.

Summary statistics will be presented throughout. For continuous endpoints, the summary statistics will generally include number of subjects with data, mean, standard deviation, median, minimum and maximum. For categorical endpoints, the summary statistics will generally include: number of subjects randomized and/or dosed, number of subjects with data, and the percentage of those with data in each category. Frequency distributions will be presented as appropriate.

The statistical software, SAS® version 9.3 or above, will be used for all summaries and statistical analyses.

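### The set called ITT is a modified ITT, and adverse events of an attempted but undelivered first lumbar puncture fall outside every by-arm adverse event table

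*Protocol*

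**What the plan says.** Protocol 3.4.2 gives the Day 1 order: children "undergo pre-dose evaluations, be randomized, and then receive either an LP injection of Study Drug (ISIS 396443) or a sham procedure". Protocol 4.3 then applies the replacement rule: "If a subject does not successfully receive the first dose of ISIS 396443/undergo the first sham procedure, they will be replaced". The synopsis words the drug-arm condition as completing the first dose, and SAP 2 and 2.2 repeat the replacement rule.

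Protocol 10.3 uses one sentence for both the ITT Set and the Safety Set: "All patients who are randomized and receive at least 1-dose of Study Drug/sham procedure". SAP 3 agrees. For efficacy, "The ITT Set is defined as all subjects who are randomized and received at least one dose of study drug/sham procedure"; the Safety Set is "comprised of all subjects who were randomized and received at least one dose of study drug or underwent one sham procedure".

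SAP 2.2 says of replaced children: "Results from these subjects will be reported in the CSR as occurring before the start of treatment and will not be included". What they are left out of, as that sentence ends, is every formal analysis.

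The procedures differ. Under Protocol 8.1 the drug arm has a needle placed at or near L3/L4, 5 mL of CSF collected and 5 mL injected; anaesthesia or sedation may be used. Under Protocol 8.2 the sham is a skin prick: "The needle will break the skin but no LP injection or needle insertion will occur". Unblinded staff perform both; for the drug arm, "ISIS 396443 will be administered by dedicated study personnel who are unblinded to treatment group".

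**The concern.** An intention-to-treat set should be fixed by randomisation. Here a child enters it only after a procedure whose demands depend on the arm. A sham child whose skin is broken has undergone the procedure and counts. A drug-arm child whose skin is broken, or whose CSF has been drawn, but who receives no injection does not count. Staff who know the assignment perform the procedure that decides this. If children with difficult lumbar access also have a different motor course, they leave the drug arm while comparable children stay in the sham arm.

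The safety side does not depend on that last assumption. A child may be sedated and punctured without receiving drug. What happens to that child is a consequence of assignment to intrathecal treatment, yet the plan classes it as occurring before treatment.

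**Working it through.** **1. The plan's own figure.** Protocol 10.2: 70 against 35, difference 3, SD 4.4, two-sided alpha 0.05, power at least 90%. Standard error = 4.4 x sqrt(1/70 + 1/35) = 0.911, and 3/0.911 = 3.29. Power is 90.9% by normal approximation and 90.4% by exact noncentral t. The claim reproduces.

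**2. Efficacy effect of the exclusion.** Inputs: 84 drug and 42 sham children (SAP 5.1) and SD 4.4. Two quantities are assumed because the documents give neither: f, the share of drug-arm children whose first injection is never delivered, and D, how much worse those children's mean change would be than that of the children kept. The all-randomised drug-arm mean is (1 - f)m + f(m - D) = m - fD, so exclusion overstates the drug-arm mean by fD. Type I error comes from shifting the test statistic by fD / [4.4 x sqrt(1/(84(1 - f)) + 1/42)] against 1.96, ignoring the interim look. The last two columns analyse everyone randomised and assume no benefit in undosed children, so the true difference is 3(1 - f).

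| f | Children dropped, 84f | Chance of at least one | Bias, D = 2 | Bias, D = 4 | Type I error, D = 4 | All-randomised difference | Power, 84 v 42 |
|---|---|---|---|---|---|---|---|
| 1% | 0.8 | 57% | 0.02 | 0.04 | 5.0% | 2.97 | 94.3% |
| 2% | 1.7 | 82% | 0.04 | 0.08 | 5.1% | 2.94 | 93.9% |
| 5% | 4.2 | 99% | 0.10 | 0.20 | 5.7% | 2.85 | 92.5% |

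With no failures, power at 84 against 42 is 94.7%. If D is negative, the bias changes sign.

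Protocol 3.3 caps the trial at 130. If the 126 in SAP 5.1 are dosed children and the cap counts everyone randomised, at most 130 - 126 = 4 were replaced. All 4 in the drug arm would be 4/88 = 4.5%, inside the assumed range. The documents do not say which count the 126 is.

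**3. Where adverse events of an undelivered first puncture go.**

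- Safety Set (SAP 3): the child is not in it, having had neither dose nor sham.
- Treatment-emergent tables (SAP 6.1): emergence is judged against receipt of the first dose or sham. There is no such date.
- Post-procedure windows of 0-6, 6-24 and 24-72 hours, and the 7-day summary of puncture-related events such as headache and back pain (SAP 6.1.6): these run from dosing or sham. There is no start point.
- What remains: serious events before treatment are listed (SAP 6.1.4), and patient listings and disposition cover all enrolled patients (Protocol 10.6, 10.6.1).

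Non-serious events of an undelivered first puncture, and of its sedation, therefore reach no adverse event comparison by arm.

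**The case against.** Several stronger readings are tempting, and the documents do not carry them.

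- *Only the lumbar puncture arm can fail.* The rule covers both arms, Protocol 3.3 foresees missed Day 1 procedures in either, and a sham child could withdraw or fall ill after randomisation. The asymmetry is an inference from the two procedures. It stands for technical failure; same-day randomisation keeps the window for other causes short.
- *Nothing in the entry criteria looks at lumbar access.* Exclusion 6 removes abnormalities that would interfere with lumbar puncture, exclusion 13 conditions that compromise study procedures, and exclusion 3 severe scoliosis. Inclusions 7 and 9 require ability to complete procedures and fitness for planned sedation. These reduce the risk; they do not remove it.
- *Any imperfect first attempt excludes the child.* The analysis sets ask for at least one dose, and SAP 7.1 and 7.2.1 expect actual doses to differ from nominal. A partial injection can therefore be read as dosed. Protocol 8.1 permits alternative levels, and SAP 2.4 sets Day 1 as the day the first dose is given, so a later successful attempt also fits. No passage gives the operator the decision to replace a child. What stands is that no text says how these cases are classified.
- *The harms disappear.* Adverse events are collected from consent (Protocol 9.4.1, 9.4.2), and the listings in step 3 remain. The by-arm comparison is lost; the data are not.
- *The drug effect is inflated.* Nothing in the documents links difficult access to HFMSE change, so size and direction both rest on assumption.

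**Conclusion.** The point holds in a limited form. By the text alone, ITT here means randomised and treated, and replaced children are outside the formal analyses. For efficacy the consequence is small: about 1 to 4 drug-arm children at an assumed 1-5% failure rate, and 0.02 to 0.20 points if they would do 2-4 points worse, against a planned 3. The documents supply neither assumption, so a reader should not infer a demonstrated bias in favour of the drug.

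The safety gap is firmer because it follows from the definitions without any assumption about prognosis. Its size still depends on how many first punctures were attempted but not delivered, which is not stated. For an intrathecal product those are events that the procedural tables should show. The change is worth making, but the gap does not threaten the primary result.

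**What to change.** **Safety Set (Protocol 10.3, SAP 3).** Define it as all randomised subjects in whom the first procedure was started (sedation given or skin broken), tabulated by arm. Undelivered first procedures go under the assigned arm. In SAP 6.1 and 6.1.6, count treatment emergence and post-procedure windows from the start of that attempt. In SAP 2.2, delete the sentence that treats replaced children as pre-treatment and excludes them.

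**ITT Set.** Define it as all randomised subjects, analysed as randomised. At minimum, add an all-randomised sensitivity analysis for the primary endpoint. Apply the same set to the group counts in the SAP 5.1 resampling.

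**Missing HFMSE in undosed children.** Use any observed follow-up. Where there is none, do not use the SAP 5.3 imputation within the drug arm: it would give undosed children the course of treated ones and restore the optimism being removed. Impute from the sham arm, or assume no improvement from baseline.

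**Wording.** Keep replacement as an accrual rule only. State, for analysis purposes, how a partial injection and a later successful attempt are classified, and reconcile the synopsis, Protocol 4.3 and Protocol 10.3.

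**Cost.** Document edits, a little extra analysis work and slight dilution of the estimate: 2.85 instead of 3 points at 5% failures with no benefit in those children, with power still 92.5%. New follow-up visits may not be obtainable. All 126 children were to have had the chance of a Day 169 visit by 31 August 2016, which puts first procedures at about 16 March 2016 or earlier (168 days before), ahead of Amendment 2 on 30 June 2016. That is why the imputation rule for undosed children matters.
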